4.6 Analysis of safety data

If not further specified, the system organ class (SOC) and preferred term for adverse events analysis will be summarized using Medical Dictionary for Regulatory Activities (MedDRA) Version 23.0 with severity grade defined by CTCAE Version 5.0.

4.7 Reporting Timeframe of Measurement for Analysis

For analyses of efficacy endpoints, the latest observation within the study day will be used. If the observations for Day 15 and Day 28 fall outside of the 24-hour window of the study day, the observation will be considered as missing and the imputation as described above will apply as appropriate.

For summary analyses of subject efficacy assessment and safety analysis, the latest observation within the study day during treatment period or within protocol defined time-windows during the follow-up period, will be used. No imputation will be made.

For safety analysis with adverse events, the observation with highest severity within the study day during treatment period or within protocol defined time-windows during the follow-up period, will be used. No imputation will be made.

4.8 General Rules for Summarizing Data

The general rules for summarizing the data, unless otherwise mentioned, are:

- Number of subjects in the defined population and numbers of subjects with available data will be provided
- Continuous variables will be summarized using descriptive statistics such as mean, standard deviation, median, minimum, and maximum.
- Categorical variables (e.g., gender, race, etc.) will be provided using frequency tabulations
- Analyses for Phase I portion and for Phase II portion will be performed separately. The analysis for Phase I will be based on safety analysis set. Analysis for Phase II will be performed by treatment group. The main analysis set for efficacy is the full analysis set, and the main analysis set for safety is the safety analysis set.

5. Randomization, Allocation Concealment and Blinding

5.1 Randomization

The Phase I study is a single-arm open label study and thus no randomization is planned.

At Phase II study, 72 subjects will be randomized to either one of the treatment arms below with randomization ratio 1:1.

- CYNK-001 with Standard of Care (SOC, also known as best supportive care) (n=36)
- SOC (n=36)

The randomization will be stratified by subject's age at baseline (less than 45 years; and greater or equal to 45 years).

The randomization sequence will be developed by a qualified FHI 360 Randomization Statistician (RS) who is not otherwise involved in the study using a validated program written in SAS®. [REDACTED]

[REDACTED] The detail about randomization plan is documented in the randomization request form (RFR) which is prepared under FHI Standard of Procedure (SOP) Document #07002.

5.2 Allocation Concealment and Blinding

Since the randomized phase (phase II) of the study is open label, no blinding after randomization is involved. To assure unbiasedness, the study statisticians will remain blinded with no access to the data of treatment arm before completion of final data cleaning.

5.3 Blinded Data Review

Prior to scheduled unblinding and final data cleaning, the data may be reviewed in a blinded fashion. Based on analysis needs, the lead statistician will develop specific listings for this review and will document the sponsor or stakeholders' decisions prior to unblinding. [REDACTED]

[REDACTED] Blinded data review may also include clinical evaluation of safety data for reasonableness or to issue clinical queries to the site if needed. Any decisions affecting analysis will be described in internal documentation and the CSR.

6. Study Size and Power

Phase I Study

Fourteen (14) subjects will be treated with CYNK-001 in the Phase I portion. This sample size is determined to be adequate for the evaluation of safety and potential efficacy, based on clinical

judgement for this coronavirus disease and the current treatment status before starting Phase II portion. This number is not driven by hypothesis testing and power calculation.

Phase II Study

The primary efficacy endpoint is time to clinical improvement on the Ordinal Scale for Clinical Improvement (OSCI) defined by the World Health Organization (WHO), at Day 15. As preliminary purpose of proof of concept, without relevant data for the new coronavirus disease, no multiplicity will be adjusted and a 1-sided α of 0.05 will be used for the sample size consideration. With a sample size of 36 for each group (72 in total with 1:1 randomization ratio), a reduction of 50% for the time to event efficacy of CYNK-001 comparing with control can be detected with a power of at least 81% (assuming the time to clinical improvement is 8 days or earlier for CYNK-001 group, and 16 days or earlier for the control group with the same reduction rate of 50%) by using Log-rank test. This estimation is based on the study design with endpoint assessment at 28 days after infusion for each subject.

7. Analysis Populations

- Screened population – include the subjects who are screened.
- Safety Population – include all subjects who receive any amount of CYNK-001 in either phase or who enroll into the control group in phase II. Subjects will be analyzed according to the actual treatment they received for safety analysis.
- ITT Population– the definition of intent-to-treat population applies to phase II only. This population includes all randomized subjects. The subject will be analyzed according to the treatment arm they are randomized to.
- Per Protocol Population (PP) - the definition of per protocol (PP) population applies to phase II only. This population includes all randomized and treated subjects who have no major protocol violations/deviations that may affect the primary efficacy outcome. Protocol violations/deviations will be identified and reviewed before database lock.

8. Data Monitoring Committee (DMC)

Periodic safety monitoring will be conducted by the DMC. The recommendation whether to continue, de-escalate, stop the trial or move to Phase II for safety or futility will be reached by the DMC based on their review of safety and efficacy information. Specific details are provided in the DMC Charter.

9. Subject Disposition and Protocol Violation/Deviation

Subject disposition (analysis population allocation, enrolled, discontinued, primary reason for discontinuation) will be summarized using frequency and percent. A summary of subjects enrolled by site will be provided.

Protocol deviations will be identified before database lock. Major protocol deviations will be summarized.

10. Demographics and Baseline Characteristics

Demographic variables such as sex, race, ethnicity and age group will be summarized using number (n) and percentage (%). Descriptive statistics such as n, mean, standard deviation (SD), median, min and max will be calculated for age. Infection symptoms at baseline will be summarized.

Medical history will be coded using Medical Dictionary for Regulatory Activities (MedDRA) version 23.0. System Organ Class (SOC) and Preferred Term (PT) will be summarized by number and percentage (%) of patients.

11. Analysis of Study Treatment Exposure

Exposure to study drug will be summarized with descriptive statistics for the number of doses received and the total cumulative dose. The number of dose interruptions will be summarized. The analysis will be based on safety population.

Individual listings will be provided.

12. Study Day Definition

Study Day 1 is defined as the day subject took the first dose of CYNK-001.

The study day of any given event is relative to Study Day 1. If an event is after the first dose, then study day is calculated as the event date minus the date of Study Day 1 + 1; if an event is before the first dose, then study day is calculated as the event date minus the date of Study Day 1.

13. Efficacy Analysis

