All subjects will be monitored for AEs during the study. **Infusion related reactions (IRRs) will be documented for the first 72 hours of CYNK-001 infusion at every dose.** Assessments may include monitoring of any or all of the following parameters: the subject's clinical symptoms, laboratory, pathological, radiological or surgical findings, physical examination findings, or findings from other tests and/or procedures.

All AEs that occur after any subject has been enrolled, before treatment, during treatment, or within 28 days following the first CYNK-001 infusion (to Study Day 28), whether or not they are related to the study, must be recorded on forms provided by Celularity.

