12.4. Reporting of Serious Adverse Events

Any AE that meets any criterion for an SAE requires the completion of an SAE Report Form in addition to being recorded on the AE page/screen of the eCRF. All SAEs must be reported to Drug Safety within 24 hours of the Investigator's knowledge of the event by facsimile, or other appropriate method (e.g., via email), using the SAE Report Form, or approved equivalent form. This instruction pertains to initial SAE reports as well as any follow-up reports.

The Investigator is required to ensure that the data on these forms is accurate and consistent. This requirement applies to all SAEs (regardless of relationship to CYNK-001) that occur during the study (from the time the subject signs Study ICF until Study Day 28) or any SAE made known to the Investigator at any time thereafter that are suspected of being related to CYNK-001. SAEs occurring prior to treatment (Screening Period) will be captured in the EDC.

The SAE report should provide a detailed description of the SAE and include a concise summary of hospital records and other relevant documents. If a subject died and an autopsy has been performed, copies of the autopsy report and death certificate are to be sent to Drug Safety as soon as these become available. Any follow-up data should be detailed in a subsequent SAE Report Form, or approved equivalent form, and sent to Drug Safety.

Where required by local legislation, the Investigator is responsible for informing the Institutional Review Board/Ethics Committee (IRB/EC) of the SAE and providing them with all relevant initial and follow-up information about the event. The Investigator must keep copies of all SAE information on file including correspondence with Celularity and the IRB/EC.

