13.1.2 Primary Efficacy Endpoint for Phase II

The primary endpoint is time to clinical improvement as measured by OSCI. Time to clinical improvement by OSCI is defined as the time from the date of randomization to the first date of clinical improvement measured by OSCI. Subjects who do not have clinical improvement on or before Study Day 28 will be censored at Study Day 28.

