14.1 Adverse Events

All AEs will be coded using the MedDRA dictionary Version 23.0 or higher. The severity of toxicities for AEs will be graded 1 to 5 according to the National Cancer Institute Common Terminology Criteria for Adverse Events (NCI-CTCAE) Version 5.0 whenever possible. AEs with missing severity will be presented in the summary table as missing category.

A treatment-emergent adverse event (TEAE) is defined as an AE which started on or after the first dosing date of the study drug or an existing condition being worse on or after the first dosing date of the IP.

Adverse events with unknown onset date and with end date after first dosing date will be counted in the TEAE.

A treatment-related AE is defined as an AE which is considered to be of suspected relationship to the study drug. Adverse events with missing relationship to study drug will be assessed as treatment-related.

The following summaries will be provided:

- A table for overall summary and a listing of all AEs by SOC and PT will be provided for AEs that occurred during the screening period.
- Separate summaries will be provided for the treatment period (Day 1 – Day 28) and follow-up period (Day 29 to 6 months). The following summary tables will be generated:
 - Overall summary
 - All TEAEs by SOC and PT
 - TEAEs that satisfy the DLT criteria (Phase I treatment period only)
 - TEAEs leading to discontinuation of treatment
 - TEAEs with toxicity grade ≥ 3
 - Drug-related TEAEs
 - Serious TEAE
 - TEAEs that led to death
 - Summary of CRS

If a subject experiences multiple AEs under the same PT (SOC), then the subject will be counted only once for that PT (SOC). If a subject experiences the same AE more than once with different toxicity grade, the event with the highest grade will be tabulated in “by maximum toxicity grade” tables.

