16.1 Analysis of Prior and Concomitant Medication

Prior medicine is defined as the medication that was given prior to the day of the first dose

Concomitant Medicine is defined as medication which is given on or after the date of first dose.

Frequency summaries of prior and concomitant medications coded with WHO drug dictionary (version Mar2020) will be provided by treatment group.

At each level of subject summarization, a subject is counted once if the subject reported one or more medications. Complete listing, including reason for use, duration, frequency and dosage of concomitant and prior medication will be provided.

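### Phase II Study Day, TEAE and concomitant medication are defined only by the first CYNK-001 dose, so control and never-dosed subjects have no reference date

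*SAP*

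**What the plan says.** **Definitions tied to the first dose**
- SAP Section 12: "Study Day 1 is defined as the day subject took the first dose of CYNK-001". Every other study day is counted from that date.
- SAP Section 14.1: a TEAE is "an AE which started on or after the first dosing date of the study drug", or a pre-existing condition that is worse on or after that date. Events with unknown onset are classified by whether they ended after the first dosing date.
- SAP Section 16.1: "Concomitant Medicine is defined as medication which is given on or after the date of first dose". Section 16.2 dates concomitant procedures from first dose too.

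**Where controls need those definitions**
- SAP Section 7 puts control subjects in the safety population, and Section 14 analyses Phase II safety by treatment arm.
- SAP Section 14.1 gives separate AE summaries for Days 1 to 28 and for Day 29 to Month 6.
- SAP Section 13.1.2 starts the primary endpoint at randomisation but adds: "Subjects who do not have clinical improvement on or before Study Day 28 will be censored at Study Day 28".

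**Collection rules in the protocol**
- Section 12.3.1.1 opens AE recording at enrolment and closes it "within 28 days following the first CYNK-001 infusion (to Study Day 28), whether or not they are related to the study".
- Section 12.3.1.2 requires SAEs to be recorded once any CYNK-001 has been given.
- Section 12.4 requires all SAEs from consent to Study Day 28 and, after that, "any SAE made known to the Investigator at any time thereafter that are suspected of being related to CYNK-001".
- Sections 12.1 and 12.3.1.7 call for monitoring throughout the study, and Table 2 sets the Phase II safety endpoint at Month 6.

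**The concern.** A control subject never has a first CYNK-001 dose, so any rule that starts from that date returns nothing for half of the randomised subjects. The tables affected include all TEAEs, grade 3 or higher, serious, and leading to death. Comparing safety between the arms is a stated purpose of Phase II, and these tables would serve it.

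Protocol Sections 6.1.1 and 6.1.2 have the same gap. Screening ends just before CYNK-001 is given, and the treatment period begins with study drug. Read literally, a control stays in screening, and SAP Section 14.1 tabulates screening-period AEs separately.

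A missing analysis date can be supplied later. Unequal collection cannot be repaired. If SAEs after Day 28 are required only when suspected of being related to CYNK-001, a control subject cannot meet the condition, and a by-arm table for Day 29 to Month 6 would compare different kinds of data.

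**Working it through.** **Step 1. Each rule applied to each kind of Phase II subject**

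| Rule | CYNK-001, dosed | CYNK-001, never dosed | Control |
|---|---|---|---|
| Start of primary endpoint (SAP 13.1.2) | randomisation | randomisation | randomisation |
| Study Day 1 (SAP 12) | first dose | none | none |
| Study Day 28 censoring (SAP 13.1.2) | defined | none | none |
| TEAE (SAP 14.1) | defined | outside safety population | none |
| Concomitant medication (SAP 16.1) | defined | none | none |
| AE recording opens (Protocol 12.3.1.1) | enrolment | enrolment | enrolment |
| AE recording closes (Protocol 12.3.1.1) | 28 days after first infusion | none | none |
| SAEs required after Day 28 (Protocol 12.4) | suspected related | cannot apply | cannot apply |

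Controls therefore have a time origin for efficacy and a start of AE recording. They lack a Study Day, and everything that depends on one.

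**Step 2. Effect on the TEAE tables**

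The documents give no expected AE incidence, so this step assumes the same true incidence in both arms and 36 subjects per arm.

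| Assumed incidence | 36 × incidence | CYNK-001, as written | Control, as written | Each arm, randomisation anchor |
|---|---|---|---|---|
| 10% | 3.6 | 4 of 36 | none countable | 4 of 36 |
| 30% | 10.8 | 11 of 36 | none countable | 11 of 36 |
| 50% | 18.0 | 18 of 36 | none countable | 18 of 36 |
| 80% | 28.8 | 29 of 36 | none countable | 29 of 36 |

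**Step 3. Effect on the primary analysis**

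Inputs from SAP Section 6: 36 per arm, one-sided alpha 0.05, 8 versus 16 days, 28 days of follow-up, stated power at least 81%. The 8 and 16 days are read as medians of exponential times (an assumption), so the hazard ratio is 0.5.

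- Events = 36 × (1 − 2^(−28/8)) + 36 × (1 − 2^(−28/16)) = 36 × 0.9116 + 36 × 0.7027 = 58.1.
- Freedman power = Φ(√58.1 × (1 − 0.5)/(1 + 0.5) − 1.645) = 81.5%. This reproduces the stated figure.

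Now let Day 28 run from first dose on CYNK-001 and from randomisation in control, with dosing g days after randomisation (g is assumed). The first term becomes 36 × (1 − 2^(−(28+g)/8)).

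- g = 1: 58.4 events, power 81.6%.
- g = 5: 59.2 events, power 82.1%.

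Even this overstates the effect. The added events fall after the last control has been censored, so they contribute nothing to the log-rank statistic.

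**Step 4. After the change**

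With Day 1 at randomisation and 28 days of follow-up in each arm, power is again 81.5%. Only the safety tables change.

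**The case against.** The strongest reply is that any competent programmer would use randomisation as Day 1 for controls. The plan does presume a control Day 1: Protocol Section 12.2 starts best supportive care on Day 1, and the Table of Events places control treatment under the Day 1 to Day 28 columns. Most of that table and its footnotes are missing from the text available here, so a control rule there cannot be excluded. What stands is that SAP Section 12 states its own definition and has no control clause. The SAP authors did separate the phases elsewhere: the NEWS2 endpoint in SAP Section 13.2 starts at randomisation, with first dose reserved for Phase I. A second convention, first dose for treated subjects and randomisation for controls, is also workable and would classify pre-dose events differently. The choice should therefore be written down.

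A reader might infer that control AEs are not collected at all. The documents do not support that. Recording opens at enrolment (Protocol 12.3.1.1), and SAEs are reported from consent regardless of relatedness (12.4). Only the closing rules depend on CYNK-001. Nor is collection after Day 28 plainly confined to related SAEs, because Protocol Sections 12.1 and 12.3.1.7 say monitoring continues. The passages conflict.

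Deaths are not lost either. All-cause mortality to Day 28 and Month 6 is already an endpoint in both arms. Controls' medication is captured through the consent-based window in Protocol Section 12.1.7, although Section 9.2 counts back from the first infusion. What controls lack is the prior/concomitant label.

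Finally, SAP Section 15 records that the trial closed with 7 subjects enrolled and dosed in Phase I, and limits the analyses to that phase. Every analysed subject has a first-dose date.

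**Conclusion.** The gap is real and matters for the Phase II safety comparison. As written, no control event is countable as a TEAE, the two AE periods and Day 28 are undefined for controls, and the closing rules for AE and SAE collection are tied to CYNK-001 while safety is to be reported to Month 6. For never-dosed subjects the gap concerns Study Day and Day 28 censoring, since they are outside the safety population.

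The effect on the primary efficacy analysis is negligible: 81.5% power against at most 82.1%, for assumed gaps of 1 to 5 days and exponential times.

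Three stronger readings are tempting and should not be drawn:
- That controls have no clock. The primary and most other time-to-event endpoints start at randomisation. What is missing is Study Day.
- That the control TEAE rate would be a true zero. Strictly, TEAE status is undefined because the reference date is missing; none countable is the literal result of applying the rule.
- That the ARDS (17%) and death (4.3% to 11%) rates in the protocol's cited series predict control events. Those were hospital series with 23% to 26% of patients in intensive care. This trial excludes mechanical ventilation and intensive-care admission for ARDS, sepsis or severe pneumonia, and may treat Phase II subjects as outpatients.

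The point concerns the Phase II plan only. No result from the closed trial is affected.

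**What to change.** 1. SAP Section 12: for Phase II, define Day 1 as the date of randomisation in both arms. Keep a separate infusion day, counted from first dose, for exposure and infusion tables. Phase I stays on first dose.
2. SAP Sections 14.1 and 16: use that Day 1 in Phase II for TEAE (including the rule for unknown onset), concomitant medication and procedures, and the two AE periods.
3. SAP Sections 13.1.2 and 13.3: censor at Day 28 on the same clock in both arms, including subjects never dosed.
4. Protocol Sections 12.3.1.1, 12.3.1.2 and 12.4: reconcile with Sections 12.1 and 12.3.1.7 so that AEs and SAEs are collected over the same window and under the same relatedness rule in both arms. Otherwise, limit the by-arm AE and SAE tables, and the Table 2 safety endpoint, to Day 28. Month 6 mortality needs no change.
5. Protocol Sections 6.1.1 and 6.1.2: state when screening ends and the treatment period begins for a control.

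The cost is a few sentences in the SAP and a short protocol clarification. If collection to Month 6 is kept, the extra SAE questions fit the existing Day 90 and Day 180 visits. Sample size and planned power do not change. The one drawback is that events between randomisation and first dose in the CYNK-001 arm will count as treatment-emergent. Showing them separately by infusion day deals with that.

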13.1 Primary Efficacy Endpoint

13.1.1 Primary Efficacy Endpoint for Phase I

The efficacy analysis for Phase I will be based on the safety analysis population.

The primary efficacy endpoint for Phase I is clinical improvement by OSCI on or prior to Day 15. Clinical improvement by OSCI is defined as at least one patient state improvement compared to baseline. If clinical improvement by OSCI is demonstrated for at least 2 out of 14 subjects on or prior to Study Day 15, and CYNK-001 is deemed to be safe, the study will move to Phase II. Otherwise, the study will be terminated.

Phase I efficacy data will be summarized by descriptive analyses for the number and proportion of subjects who achieved clinical improvement by OSCI by Day 15.

The proportion of the clinical improvement by OSCI at Day 15 will be summarized with a point estimate, standard error and a 95% confidence interval.

Patients who do not achieve at least one patient state improvement will be considered as failure to improve by OSCI. No formal hypothesis testing will be carried out for this part of the analysis.

Subject listings of clinical status using OSCI will be provided.

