As a preliminary proof of concept study without relevant data for the new coronavirus disease, 1-sided α of 0.05 will be used in the sample size consideration. With a sample size of 36 for each group (72 in total with 1:1 randomization ratio), a reduction of 50% for the time to event efficacy of CYNK-001 comparing with control can be detected with a power of at least 81% (assuming the time to

clinical improvement is 8 days or earlier for CYNK-001 group, and 16 days or earlier for the control group with the same reduction of 50%) by using Log-rank test. This estimation is based on the study design with a maximum follow up of 28 days for each subject for primary analysis.

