6.1.2. Treatment Period (Day 1 to Day 28)

The treatment period begins with the administration of study drug on Study Day 1. For those subjects who are allocated treatment to CYNK-001, the initial dose will consist of 150×10^6 cells followed by the second and third doses each of 600×10^6 cells administered intravenously (IV). Subjects will receive a minimum of two and up to three CYNK-001 infusions. CYNK-001 infusions will occur on Study Days 1, 4, and 7. After the first dose, subsequent infusions on Days 4 and 7 will be provided only if no toxicity of Grade 3 and above (either related or unrelated to CYNK-001) is observed for each subject. If any such \geq Grade 3 toxicity is observed, the second and third doses will be delayed up to 48 hours until the noted event is resolved or reduced to Grade 1 toxicity level.

Subjects treated in Phase I will receive all planned CYNK-001 infusions in the inpatient setting and may be discharged one day following the final planned CYNK-001 infusion (i.e., discharged on Study Day 8, where infusions occur on Days 1, 4, and 7). If any dose is delayed, subjects will remain inpatient until one day following the final CYNK-001 infusion.

As part of discharge criteria, the study team should assess for further monitoring of subjects who may be experiencing toxicity of Grade 3 and above (either related or unrelated to CYNK-001) at the time of discharge and consult with the treating physician. The decision to discharge a subject should be in consultation with the treating physician. Physicians should follow best clinical practice to determine appropriate timing of hospital discharge.

Upon discharge, plans should be made for appropriately delegated staff to have telephone contact with subjects every day between hospital discharge through at least Day 15 visit for safety/AE monitoring.

Subjects will be provided with a thermometer, pulse oximeter, and blood pressure monitor for at home collection of temperature, oxygen saturation, and blood pressure with written instructions on their use as well as expectations for self-monitoring. These daily measurements will be reported via telephone to the clinical staff during each daily telehealth visit. During these daily telehealth visits, subjects are to report any new symptoms or worsening of symptoms associated with previously identified adverse events.

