14.6. Efficacy Analysis

Phase I efficacy data will be summarized by descriptive analyses. The efficacy endpoints used in the lack of efficacy tests is the responses at Day 15 of the clinical improvement by OSCI. If efficacy is not established in 2 out of the 14 subjects, the study will be terminated. If efficacy is noted in 2 or more subjects, the study will move forward to the Phase II portion.

Efficacy endpoints are defined in [Section 6.9](#).

Phase II efficacy data will be summarized by descriptive analyses. The efficacy endpoints used in the lack of efficacy tests is the responses at Day 15 of the clinical improvement by OSCI. If efficacy is not established in 2 out of the 14 subjects, the study will be terminated. If efficacy is noted in 2 or more subjects, the study will move forward to the Phase III portion.

No interim analysis will be implemented in this study.

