14.10. Study Stopping Rules

Phase I of the study:

a. Safety Stopping Rules:

In addition to the evaluation of vital signs, performance status, a Consultation with the Medical Monitor is required prior to each CYNK-001 infusion if there is:

- an increase in supplemental oxygen of greater than or equal to 50% from baseline (for first CYNK-001 infusion) or from level at prior CYNK-001 infusion (for second and third CYNK-001 infusion) resulting in oxygen use of greater than 8L.

-or-

- a change in the mode of supplemental oxygen delivery with the intention to deliver oxygen more efficiently.

The Medical Monitor will escalate to the Sponsor clinical and safety team as appropriate per GCP guidelines to advise if a subject who is experiencing rapid worsening of disease should proceed to first or subsequent CYNK-001 infusion.

b. Study Stopping Rules:

- During Phase I, 3 subjects will be initially monitored for any potential DLTs until 24 hours after the final dose given to the 3rd subject. If any DLTs occur, the DMC will be convened. Study will proceed to enroll the remaining 11 subjects if it is deemed safe in the first 3 subjects. For the remaining 11 subjects, DMC will be convened if the safety stopping rule which is defined as death in any of the subjects irrespective of relatedness to the product is met. Overall, in case of 2 out of the 6 subjects had experienced DLTs in the Phase I portion of this study, the DMC will be convened for safety evaluation.

- The study will be stopped, and DMC will be convened, if death in any of the 14 subjects had occurred by Study Day 15 from the first dose of CYNK-001 infusion irrespective of relatedness to CYNK-001. If no such events have occurred in all 14 subjects, it is deemed safe to proceed to Phase II of the study.
- All other serious adverse events assessed as “Related to product” will be tracked and sent for DMC review and recommendation but will not trigger the study to be stopped unless recommended by the DMC Chair.
- Worsening of a condition in any subject will be tracked and sent for DMC review and recommendation but will not trigger the study to be stopped unless recommended by the DMC Chair.

b. Efficacy (Futility) Stopping Rules:

By Day 15 of CYNK-001 infusion in the Phase I, the study may stop for futility if there is less than 2 subjects with clinical improvement of at least one “Patient State” category as defined by the OSCI ([Appendix D](#)).

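### On the plan's own control assumption, the Phase I rule of at least 2 of 14 improved by Day 15 cannot tell CYNK-001 from background recovery: an inert product passes about 99.7% of the time

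*SAP*

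**What the plan says.** The response is a change on the WHO ordinal scale: "Clinical improvement by OSCI is defined as at least one patient state improvement compared to baseline" (SAP 13.1.1). The same section moves the study to Phase II "If clinical improvement by OSCI is demonstrated for at least 2 out of 14 subjects on or prior to Study Day 15", provided that the product is also deemed safe, and otherwise terminates it. Protocol 5.1, Table 2 (where it is labelled a futility check) and 14.10 carry the same threshold. Its force varies. SAP 13.1.1 and Protocol 14.6 make termination mandatory below the bar, while in Protocol 14.10 "the study may stop for futility if there is less than 2 subjects with clinical improvement", and the synopsis and SAP 3 are equally permissive. The synopsis and Protocol 5.1 describe reaching the bar as efficacy having been demonstrated.

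Both documents say that n = 14 does not rest on hypothesis testing or a power calculation. Neither gives a background improvement rate for the rule.

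The only background figure is in the Phase II sample-size text (protocol synopsis; SAP 6). It puts improvement on the product at 8 days at the latest. For control, SAP 6 has "16 days or earlier for the control group with the same reduction rate of 50" per cent. With 36 per arm, one-sided alpha 0.05 and 28 days of follow-up, the stated log-rank power is at least 81%.

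The Phase II paragraph of Protocol 14.6 repeats the 2-of-14 rule and adds: "If efficacy is noted in 2 or more subjects, the study will move forward to the Phase III portion".

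**The concern.** With no concurrent control, a response count means something only against the rate expected without the drug. If the plan expects close to half of untreated subjects to improve by Day 15, a bar of 2 in 14 (14%) lies far below that. Almost any product that does not harm recovery would clear it.

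This is the only numeric efficacy criterion before a further 36 subjects are assigned to CYNK-001. A pass could be quoted as evidence of activity when it mostly reflects the natural course of the illness.

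**Working it through.** **Inputs.** Rule: at least 2 of 14 (SAP 13.1.1). Times to improvement: 16 days on control, 8 days on CYNK-001 (SAP 6). Phase II: 36 per arm, one-sided alpha 0.05, 28 days. Day count: SAP 12 makes the first dose Day 1, so Day 15 is 14 elapsed days; 15 days is shown as a variant. Assumptions of this check: the times are medians, and the curve is exponential.

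**Step 1: reproduce the plan's own figure.** The proportions improved by 28 days are 1 − 2^(−28/16) = 0.703 on control and 1 − 2^(−28/8) = 0.912 on CYNK-001. Expected events are 36 × (0.703 + 0.912) = 58.1. By Freedman's formula with hazard ratio 0.5, z = √58.1 × (1 − 0.5)/(1 + 0.5) − 1.645 = 2.541 − 1.645 = 0.896, so power is 81.5%. This matches the stated 81%. Reading the times as exponential means gives 85.0% by the same formula, so the median reading fits better.

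**Step 2: improvement by Day 15 without drug effect.** p0 = 1 − 2^(−14/16) = 0.455 (0.478 at 15 days).

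**Step 3: chance that an inert product passes.** P(X ≥ 2) = 1 − (1 − p0)^14 − 14·p0·(1 − p0)^13 = 1 − 0.0002 − 0.0024 = 0.9974. At 15 days it is 0.9985. An inert product is stopped in 0.15% to 0.26% of trials.

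**Step 4: sensitivity.**

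| Background assumption | Rate by Day 15 | P(pass 2 of 14) |
|---|---|---|
| Exponential, 14 elapsed days | 45.5% | 99.7% |
| Exponential, 15 days | 47.8% | 99.85% |
| Weibull, median 16 days, shape 0.5 to 4, 14 or 15 days | 33% to 49% | 97.3% to 99.9% |
| Discharged in the 99-case series cited in Protocol 4.1 | 31% | 96.0% |
| Discharged in the 138-case series cited there | 34.1% | 97.6% |

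The two discharge proportions are at each paper's data cut-off, not at Day 15, and serve only as a rough lower check.

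**Step 5: where the rule does stop.** At a true rate of 5% it passes 15.3% of the time; at 10%, 41.5%; at 20%, 80.2%; at 30%, 95.3%. Passing and stopping are equally likely at about 11.7%.

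**Step 6: bars available with the same 14 subjects.** At 14 elapsed days the 8-day target gives p1 = 1 − 2^(−14/8) = 0.703. For a Weibull shape of 0.5 with the same medians, p0 = 1 − 2^(−(14/16)^0.5) = 0.477 and p1 = 1 − 2^(−(14/8)^0.5) = 0.600.

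| Bar | Inert passes | Product at 8-day target passes | Wrong stop, exponential | Wrong stop, shape 0.5 |
|---|---|---|---|---|
| ≥2 | 99.7% | >99.9% | <0.1% | <0.1% |
| ≥7 | 47% | 97% | 3% | 15% |
| ≥8 | 27% | 91% | 9% | 31% |

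**The case against.** **The rule is not meant as a test.** The documents present it as a check for lack of efficacy, disclaim formal testing and do not base n on power. That explains why no error rate is given. It does not change what the rule can detect, and it does not fit with calling a pass a demonstration of efficacy.

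**The rule can stop.** A reader might infer that it never could. That is too strong: it stops 85% of the time at a true rate of 5% and 58% at 10%. The defect is that these rates are far below what the plan expects without the drug.

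**It is not the only look at efficacy.** Protocol 14.11.2 has the DMC review safety and efficacy data after Day 15 of the last Phase I subject, SAP 8 gives it a futility recommendation, and the safety condition must also be met. All of this stands. But neither document gives the DMC a different numeric efficacy criterion.

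**The 16-day figure is soft.** It was set without relevant data, for a Phase II that may include outpatients, whereas Phase I is inpatient. This is fair, and the reason for the sensitivity range. The conclusion does not depend on the exact value.

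**Discharge as response.** In Appendix D, moving from mild hospitalized disease to ambulatory is one Patient State, and Phase I subjects "will receive all planned CYNK-001 infusions in the inpatient setting and may be discharged one day following the final planned CYNK-001 infusion". A reader might infer that scheduled discharge manufactures responses. The documents do not show how many subjects would be in hospital only for infusion, and they leave discharge to clinical judgement, so the effect cannot be sized. Rescoring subjects by medical need would replace the WHO descriptors and is not warranted.

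**Protocol 14.6.** As printed, its Phase II paragraph conflicts with the ITT stratified log-rank analysis in the synopsis and SAP 13.3, and it names a phase that the design does not contain. In the text at hand, the 14.7 heading and the Phase II part of 14.8 are absent next to it. Treating it as a settled drafting error would go too far before the source PDF is checked.

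**Conclusion.** The point holds as a design weakness. On the plan's control assumption, the 2-of-14 rule passes an inert product 99.7% of the time (99.85% at 15 days), and 97% to 99.9% of the time across the Weibull shapes tried. It cannot separate CYNK-001 from background recovery. This rests on 16 days being a median, which the reproduced 81% power supports, and on the assumed curve shape. The words that allow an earlier control time would, if anything, raise the pass rate. The calculation covers the efficacy condition only, and no dropout is applied because none is stated.

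A reader might also infer that subjects entered Phase II on the strength of this gate, or that a correction is mandatory. SAP 15 records that the sponsor closed the trial after 7 Phase I subjects, and its reduced analysis list contains no go/no-go assessment. The gate was not reached, so the consequence is limited to the plan as written, any report that describes the rule, and any reuse of it.

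**What to change.** 1. Derive the threshold from the 16-day and 8-day assumptions and state its false-go and false-stop probabilities at 14 elapsed days, with a sensitivity to curve shape. At least 7 of 14 or at least 8 of 14 are examples (last table under the working). The choice between them is the sponsor's trade-off; even the stricter one passes an inert product about 27% of the time.
2. If 2 of 14 is kept, state that an inert product passes it about 99.7% of the time on the plan's control assumption, and do not describe a pass as demonstrating efficacy.
3. Use one wording, mandatory or permissive, for what happens below the bar.
4. At most, report how many responders qualified only through discharge after the final infusion, leaving the OSCI scoring unchanged.
5. Secondary, after checking the source PDF: in Protocol 14.6, replace the Phase II paragraph with the ITT stratified log-rank analysis already in the synopsis and SAP 13.3.

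The cost is protocol and SAP wording, with no added subjects. A higher bar brings about a 3% (≥7) to 9% (≥8) chance of stopping a product that meets the 8-day target, or 15% to 31% under a Weibull shape of 0.5. With the trial closed, items 1 and 3 matter only if the design is reused; the disclosure in item 2 can still go into the report.
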